### **3.4 Pre-treatment Evaluation and Management**

The following tests/evaluations will be completed prior to initiation of treatment:

- 1) Informed consent: If determined that patient has cognitive impairment which includes decision making capability, a LAR will be used as appropriate for this potentially vulnerable population.
- 2) Consultation with Co-Investigators(Geriatrics/Neuro Specialists) to assess suitability.
- 3) The mini-mental state examination (MMSE)
- 4) The Alzheimer's Disease Assessment Scale2r-Cognitive Subscale(ADAS-Cog)
- 5) Baseline Quality of life questionnaires (QOL-AD; QUALID)
- 6) Pre-treatment Amyvid PET/CT Scan
- 7) Consultation with Radiation Oncologist Investigator prior to enrollment
- 8) History and Physical

### **3.5 Pretreatment Evaluation of Cognitive Status**

Candidate patients for the study will undergo assessment of general and neurologic history, physical and neurologic examinations and administration of the following psychometric or behavioral tests: the Alzheimer's Disease Assessment Scale2r-Cognitive Subscale (ADAS-Cog) and the mini-mental state examination (MMSE).

The mini-mental state examination (MMSE) and the Alzheimer's Disease Assessment Scale Cognitive scales (ADAS-Cog) have been the most widely used in clinical trials of AD treatments. The MMSE is a sensitive, valid and reliable 30-point questionnaire that is used extensively in clinical and research settings to measure cognitive impairment. It is commonly used to screen for dementia. It is also used to estimate the severity and progression of cognitive impairment and to follow the course of cognitive changes in an individual over time; thus making it an effective way to document an individual's response to treatment.

Administration of the test takes between 5–10 minutes and examines functions including registration, attention and calculation, recall, language, ability to follow simple commands and

orientation. The ADAS-Cog test is more thorough than the Mini Mental State Exam, and it primarily measures language and memory. The ADAS-Cog consists of 11 parts and takes approximately 30 minutes to administer. It is suggested that a change of 4 or greater in the MMSE is needed before results can be considered different from random events whilst results changes greater than 7 in the ADAS-Cog have been proposed to represent clinically significant changes.

### **3.6 Pretreatment Amyvid PET/CT Scan**

Amyvid (Florbetapir-F18) is a radiopharmaceutical compound approved by the FDA as a diagnostic tool in AD. Amyvid binds to amyloid- $\beta$  with a half-life of 110 minutes. The tracer significantly accumulates more in brains of patients with AD particularly in the regions known to be associated with amyloid- $\beta$  deposits [57]. A negative Amyvid scan indicates sparse to no amyloid- $\beta$  neuritic plaques and is inconsistent with a neuropathological diagnosis of AD at the time of image acquisition. A positive Amyvid scan indicates moderate to frequent amyloid neuritic plaques; neuropathological examination has shown this amount of amyloid neuritic plaque is present in patients with AD, but may also be present in patients with other types of neurologic conditions as well as older people with normal cognition. Amyvid will be administered at a dose of 370 MBq (10 mCi) administered as a single intravenous bolus in a total volume of 10 mL or less. Following the injection, an intravenous flush of 0.9% sterile sodium chloride will be administered. A 10-minute PET image will be acquired starting 30 to 50 minutes after Amyvid intravenous injection. The patient will be supine and the head positioned to center the brain, including the cerebellum, in the PET scanner field of view. Reducing head movement with tape or other flexible head restraints may be employed. Image reconstruction will include attenuation correction with resulting transaxial pixel sizes between 2 and 3 mm. Amyvid images will be interpreted only by the study designated board certified nuclear radiologist. The current guidelines for display and interpretation of Amyvid images will be followed (Appendix VII). Briefly, images will be displayed in the transaxial orientation with access as needed to the sagittal and coronal planes. In reviewing the images, all transaxial slices of the brain will be included using a black-white scale with the maximum intensity of the scale set to the maximum intensity of all the brain pixels. The brain slice with the highest levels of image contrast (highest radioactivity signals for Amyvid uptake) will be located and the contrast adjusted appropriately. Image interpretation will be initiated by displaying slices sequentially from the bottom of the brain to the top. Image interpretation is based upon the distribution of radioactive signal within the brain; clinical information is not a component of the image assessment. Images are designated as positive or negative by comparing the radioactivity in cortical gray matter with activity in the adjacent white matter.

### **3.7 Radiation Simulation**

Simulation will occur following pretreatment assessments. The patient will be simulated in the supine position, with the shoulders down and the head in neutral position. Non-contrast treatment planning CT will be acquired with the patient in the treatment position. Serial axial images with 2 mm slice thickness will be taken and span the entire head, from at least 5 cm beyond the cranial extent of the skull to the caudal aspect of the seventh cervical vertebral body.

### **3.8. Low Dose Fractionated Whole Brain Radiation Therapy**

#### **3.8.1. Equipment**

Treatment will be delivered via a linear accelerator.

#### **3.8.2. Target Volume**

The target volume consists of the entire brain and meninges, including the frontal lobe as well as the posterior halves of the globes of the eyes, with the optic disk and nerve, superior to the vertex and posterior to the occiput. The caudal border shall be below the skull base at the top of the C2 vertebral level

#### **3.8.3. Localization**

The planning target volume shall be defined by means of a simulator

#### **3.8.4. Dose Prescription and Delivery**

The prescription point in the cranial volume is at or near the center. NOTE: regardless of the location of the central axis, the dose should be prescribed at the center on the cranial volume (midway between the maximum separations). The total dose to the prescription point will be 10 Gy for the initial 15 patients then 20 Gy for patients 16-30. This dose will be delivered in 5 fractions or 10 fractions of 2 Gy. All radiation fields shall be treated once each day. The treatment shall be given 5 days a week. No corrections for bone attenuation shall be made. The dose variations in the target volume shall be within +7% (- 5% of the prescription-point dose). No corrections shall be made for treatment interruptions less than 3 days. For interruptions greater than seven days, please contact the site PI.

#### **3.8.5. Treatment Technique**

It is recommended that the patient be treated supine. The use of Aquaplast immobilization mask is encouraged but not mandatory. The cranial volume is treated with two lateral, equally weighted photon beams. The fields shall extend at least 1 cm beyond the periphery of the scalp. "Compensating beams" that block hot spots (these hot spots are typically present along the midline due to less tissue present in these regions compared to mid-brain) are allowed to achieve better dose homogeneity. Field shaping shall be done with blocks that are at least 5 half-value layers (HVL) thick. Multi-leaf collimation is allowed.

### **3.9. Radiation On-Treatment Monitoring and Adverse Events**

Radiotherapy will be continued without interruption if at all possible as prescribed. If the sum of total radiotherapy interruptions exceeds seven normally scheduled treatment days, the treatment will be considered an unacceptable deviation from the protocol. This patient should

be reported to the principal investigator, and the patient will not be considered for final data analysis. Patients who do not complete a complete, total course of study radiotherapy will be replaced in the study in order to have 15 evaluable patients in each arm.

Patients will be monitored weekly by the treating radiation oncologist for the duration of radiotherapy and at regular intervals following radiotherapy. Scheduled post treatment visits are at 6 weeks, 3, 6 and 12 months. At each visit, the patient will undergo an interval history and physical exam and completion of Common Terminology Toxicity Criteria (Version 5.0), and RTOG toxicity scoring to assess any toxicity associated with this study. The RTOG toxicity scoring is done as radiation/oncology standard of care at Beaumont. This will include not only the effects on the CNS but any general adverse effects which may or may not be related to the treatment delivered. Each patient will be assigned a baseline score for skin, eye, ear and CNS and this will be monitored and evaluated during and after treatment for both acute and late toxicity. All adverse events will be recorded on an Adverse Event Reporting Form. The known risks associated with whole brain irradiation at the dose levels described may include, but are not limited to 1) hair loss, 2) decreased hearing, 3) nausea, 4) vomiting and 5) visual changes and 6) skin reactions. The grade or severity of adverse event that is common with the planned radiation dose for this trial based on the RTOG Common Toxicity Criteria are skin (Grade 1), CNS (Grade 1), ocular (Grade 0) and brain (Grade 1). All related/possibly related Grade >3 Toxicities will be reported as unexpected in severity to the IRB and monthly to the DSMB.

If at any time during the study there is an increase of 2 or more points, an evaluation by the DSMB will take place within the week to determine if it is therapy related or due to other non-study related events. Should this happen during the course of the treatment, therapy will be immediately stopped and all medical attempts will be made to correct the cause of the noted decline. The records and information related to the event will be reported to the IRB and the FDA using standard reporting mechanism. If it is determined that the toxicity was not study related accrual will resume once cleared by IRB.

Supportive management of symptoms (e.g., the use of oral or intravenous steroids for brain edema and the use of antiemetics) is permitted at the discretion of the treating radiation oncologist, neurologist or neurosurgeon.

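### Section 3.9 removes long-interrupted patients from the final analysis and replaces non-completers without keeping either group in the toxicity rate, which is the primary endpoint

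*Combined protocol and SAP*

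**What the plan says.** Section 3.9 contains two rules on who counts.

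- **Interruption.** "If the sum of total radiotherapy interruptions exceeds seven normally scheduled treatment days", the case is an unacceptable deviation and "the patient will not be considered for final data analysis". No exception is made for safety data.
- **Non-completion.** Patients who do not finish the course "will be replaced in the study in order to have 15 evaluable patients in each arm". The term evaluable is not defined, and nothing says whether a replaced patient stays in the numerator and denominator for toxicity.

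The same section collects safety data broadly: "All adverse events will be recorded on an Adverse Event Reporting Form", covering "any general adverse effects which may or may not be related to the treatment delivered", and "Each patient will be assigned a baseline score for skin, eye, ear and CNS". It also links toxicity to stopping. On a rise of 2 or more points: "Should this happen during the course of the treatment, therapy will be immediately stopped". It adds: "If it is determined that the toxicity was not study related accrual will resume once cleared by IRB".

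Section 2.3 makes toxicity and adverse events by CTCAE v5.0 the primary endpoint, supplemented by MMSE and ADAS-Cog. Section 3.1 gives one-sided upper limits of 26.4%, 18.1% and 14.2% (99%, 95%, 90%) for zero events in 15 patients. It presents them as a safeguard against concluding from few patients that the treatment is harmless. The available text defines no all-treated safety set. Section 5.0 breaks off mid-sentence in the public copy, and nothing is inferred from what is missing.

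**The concern.** Failing to complete radiotherapy is not independent of the outcome being measured, because toxicity can itself end treatment. If patients who stop early leave the final count and others take their places, the reported toxicity rate describes those who tolerated the full course, not those who were treated. That rate can be biased downward.

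The wording also allows two primary results from one data set. One analyst could report the rate among the 15 evaluable patients in a group, another the rate among all who received radiation, and each could cite section 3.9. With groups this small, one patient changes the message: a reported 0/15 that omits a treated patient with an event gives exactly the reassurance that section 3.1 warns against.

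**Working it through.** **1. The plan's own figures.** Inputs from section 3.1: n = 15, zero events, one-sided limits. With zero events the exact upper limit is 1 − α^(1/n):

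- 99%: 1 − 0.01^(1/15) = 26.4%
- 95%: 1 − 0.05^(1/15) = 18.1%
- 90%: 1 − 0.10^(1/15) = 14.2%

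All three reproduce.

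**2. The same limits under each reading.** For x events in n patients the exact one-sided limit at confidence c is the c-quantile of a beta distribution with parameters x + 1 and n − x. The documents give no rate of interruption or non-completion, so the counts below are assumed. An event here means something uncommon, such as Grade 3 or higher.

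| Situation | Count | 99% | 95% | 90% |
|---|---|---|---|---|
| Completers only | 0/15 | 26.4% | 18.1% | 14.2% |
| All treated; one replaced patient, with an event | 1/16 = 6.3% | 34.9% | 26.4% | 22.2% |
| All treated; one replaced patient, no event | 0/16 | 25.0% | 17.1% | 13.4% |

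The figure 26.4% appears twice by coincidence: it is the 99% limit for 0/15 and the 95% limit for 1/16. With two replaced patients who both had events, the 95% limit is 32.6% (2/17); with three it is 37.7% (3/18).

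**3. Reach of the interruption rule.** More than seven means at least 8 missed scheduled days. Section 3.8.4 gives courses of 5 or 10 fractions: 8/5 = 160% of the shorter course and 8/10 = 80% of the longer. The rule will rarely be triggered, so replacement carries the practical weight.

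**4. How a patient with an event could be replaced.** Section 3.9 provides for resumed accrual after a rise of 2 or more points only when the toxicity is judged not study related. That leaves three routes:

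- events judged unrelated, which section 3.9 still records and section 2.3 does not exclude from the endpoint;
- rises of less than 2 points, for example from a baseline score of 2 to Grade 3, where the patient then stops for some further reason;
- withdrawals.

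**5. The Grade 3 stopping count.** The Schema and section 3.12 set this at more than 3 of 15 in either group and do not say how patients count once replacements take the number treated above 15. An uncounted patient changes the outcome only when that patient separates 3 from 4.

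**The case against.** The only explicit exclusion is the interruption rule, which is close to inert. On replacement the plan is merely silent: replacing a patient is not the same as removing that patient from the toxicity analysis, and sections 2.1 and 2.3 do not restrict toxicity to completers. Every adverse event is recorded, the DSMB reviews cumulative data, and a treatment-attributed death or a Grade IV event in any patient stops the study. The analysis is descriptive (section 3.1), the upper limits there justify the sample size, and no stated decision turns on 18.1% versus 26.4%. Zero adverse events of any grade is implausible anyway, since section 3.9 expects Grade 1 skin and CNS effects. Finally, a patient who stops after one fraction contributes little exposure, and follow-up is timed from completion of therapy.

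Much of this stands as a limit on reach. The interruption rule is rare, the size is hypothetical, and event capture is not in doubt. But recording and monitoring do not determine who enters the final rate. Replacing patients in order to reach 15 evaluable implies that the replaced patient is not evaluable, and the sentence before it shows that the plan is prepared to drop treated patients outright. A descriptive rate still needs a defined denominator. The exposure point is a reason to show both rates, not to leave the set undefined.

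**Conclusion.** The concern holds and should be fixed. As written, section 3.9 excludes some treated patients from the analysis of a trial whose primary endpoint is toxicity, and it leaves open whether others are counted. The direction of the risk is downward bias in the reported rate. As an illustration, one omitted patient with an event separates a 95% limit of 18.1% from one of 26.4%, a difference of 8.3 percentage points. If the omitted patient had no event, the limit would move slightly the other way, to 17.1%.

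These figures rest on assumed counts, and no actual amount of bias is claimed. Stopping for a treatment-attributed death or a Grade IV event is unaffected. The conclusion also depends on the available text containing no definition of a safety set.

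**What to change.** Add one paragraph to the analysis text:

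- Define the safety set as every patient who receives at least one fraction, by dose level, whatever the interruptions or completion.
- Use it for the primary toxicity endpoint, for the exact one-sided upper limit at the observed count, and for MMSE and ADAS-Cog where section 2.3 uses them as safety information.
- Confine the exclusion of interrupted patients and the 15-evaluable set to the secondary cognitive, quality-of-life and PET summaries.
- Show the completers-only toxicity rate beside the all-treated rate, since early stoppers contribute little exposure.
- State the date from which follow-up is counted for a patient who stops early.

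The sponsor should also reconcile the denominator of 15 in the Grade 3 stopping rule (Schema and section 3.12), and the allocation of the first 15 patients and of patients 16 to 30 in section 3.8.4, with a number treated that replacement can raise above 15 per dose level. No threshold or clinical rule is proposed here.

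The cost is wording; no patients are needed beyond the replacements already planned. The downside is a less favourable reported rate and limit if a replaced patient had an event.

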However, at the doses of radiation initially being used in this study (10 Gy) we are unlikely to evoke the common toxicity criteria seen at higher doses. Therefore, we have used the approach of Carter and Woolson [56] whose simple expression has utility for the generation of confidence intervals when zero events are observed. Fig. 2 illustrates, for relatively small sample sizes, there is a large amount of uncertainty. It is critical to convey this uncertainty in the findings and to guard against inferring a potential treatment is harmless when no adverse effects of interest are observed with limited data. Based on this relationship we have chosen an initial cohort of 15 patients to be enrolled in the first treatment scheme (2 Gy x 5 fractions). The first cohort of patients will be followed for 12 months after completion of treatment to assess safety and any toxicity/adverse events associated with treatment. Using this approach, [name] (biostatistician) has calculated the upper confidence limits for the event rate when there are 0 events in a group of fifteen distinct patients. The method is consistent with what appears in the classical statistical literature for one-sided confidence limits. Supposing that no events are observed in the results from 15 distinct patients, then the following statements can be made:

- With 99% confidence, the true underlying adverse event rate  $\pi$  does not exceed 26.4%.
- With 95% confidence, the true underlying adverse event rate  $\pi$  does not exceed 18.1%.
- With 90% confidence, the true underlying adverse event rate  $\pi$  does not exceed 14.2%.

The second treatment arm will not be used until the last patient in the first dose arm has completed all follow up. At that point a second cohort of 15 patients will be enrolled in the second dose arm (2 Gy x 10 fractions). The second cohort will undergo a similar stand-alone post-treatment assessment. The starting dose group was chosen as the regimen most commonly used in our pre-clinical studies of AD whilst, the 2 Gy x 10 fractions was chosen as it represents the most commonly used protocol to treat systemic amyloidosis and was the most effective schedule in our preclinical studies of plaque reduction (Table 1) .

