## RESULTS

### Overview

For each of the measures, we performed analyses designed to address each of the issues raised in the introduction. To assess reliability, both Pearson and Spearman correlation coefficients were calculated but, because the two measures were very close in every case, only results from the Pearson calculations are reported. Similarly, the effect of confounds due to age and education were also estimated by Pearson correlations. The effect of learning on each measure was examined by looking at change over 1 month, a time period during which little meaningful clinical change would usually occur. A more detailed analysis of the effects of repeated exposure comparing the two testing schedules is beyond the scope of this first report. The ability of each test and measure to assess the full range of dementia severity was examined by looking at the extent to which scores differed across all severity groups and the extent to which there were ceiling or floor effects. Ability to measure longitudinal change was assessed by looking at 12-month change. For some measures a difference effect size measure ( $d$ ), defined as the mean change divided by the standard deviation of the change, was used to provide an index of the relative sensitivity of that measure to longitudinal change. The value of this measure is that it takes mean change scores, which are originally expressed in different units (e.g., seconds, errors, number of words recalled), and expresses each in terms of standard deviation units, thus enabling us to compare across measures. As for any longitudinal study, data are sometimes not available for follow-up visits owing to missed visits, untestability, or errors in data recording. In each of the data tables discussed below we have listed, along with mean performance data, the number of patients in each group for whom valid data were available at baseline and at 12 months. The overall rate of missing data was low but increased with severity of dementia and duration of follow-up.

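### Section 3.9 defines the 15 evaluable patients per arm by radiotherapy delivery alone, so irradiated patients can leave the safety analysis and the zero-event limits of section 3.1 are not assured of 15 patients observed for 12 months

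*Combined protocol and SAP*

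**What the plan says.** Section 3.1 (Dose Levels and Sample Size Calculation) chooses 15 patients per dose group from the width of a zero-event confidence limit. It describes the observation period first: "The first cohort of patients will be followed for 12 months after completion of treatment", for the purpose of assessing safety. It then says that the biostatistician "has calculated the upper confidence limits for the event rate when there are 0 events in a group of fifteen distinct patients", and words the results conditionally: "Supposing that no events are observed in the results from 15 distinct patients", the true rate does not exceed 26.4%, 18.1% or 14.2% with 99%, 95% or 90% confidence.

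Section 3.9 (Radiation On-Treatment Monitoring and Adverse Events) decides who makes up the 15. It has two rules, both about delivery of radiotherapy:

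- A patient whose interruptions total more than seven scheduled treatment days is left out of the final data analysis.
- A patient who does not finish the full course "will be replaced in the study in order to have 15 evaluable patients in each arm".

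The same section says that therapy is stopped at once if there is a rise of two or more points during treatment. It schedules toxicity visits at 6 weeks and at 3, 6 and 12 months.

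The documents do not define evaluable in terms of follow-up. They make no allowance for dropout, and they do not say how a patient lost after radiotherapy enters the safety denominator.

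**The concern.** The primary endpoint (section 2.3) is toxicity and adverse events, with grade 3 or higher as the reportable level. A safety analysis should contain everyone exposed to the treatment, and an upper limit for a 12-month rate should rest on patients whose 12-month outcome is known. The plan falls short on both counts.

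**Patients with toxicity can leave the analysis.** A patient whose treatment is stopped for toxicity and not completed is replaced. One whose interruptions exceed seven treatment days is excluded outright. The patients most likely to have had a problem are therefore the ones section 3.9 removes from the 15.

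**The 15 are not assured of 12-month observation.** A patient who completes every fraction and withdraws two months later is not replaced. If zero events were then reported with the 15-patient limit, the bound would be too favourable for a 12-month rate. Section 2.3 puts the best period for assessing cognitive impairment at more than 6 months to 1 year, which is the period an early withdrawal misses.

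Section 3.1 itself warns against inferring that a treatment is harmless from limited data, and the second dose group opens only after the first has completed follow-up.

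**Working it through.** **Inputs.** From section 3.1: 15 patients, 0 events, one-sided confidence 90%, 95% and 99% (α = 0.10, 0.05, 0.01), and 12 months of safety follow-up. From section 3.9: the replacement and exclusion rules. The documents give no rate of loss, so one to three losses out of 15 is an assumed range.

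**Step 1: reproduce the plan's figures.** With zero events in n patients, the exact upper limit p solves (1 − p)^n = α, so p = 1 − α^(1/n). At n = 15:

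- 90%: 1 − 0.10^(1/15) = 14.2%
- 95%: 1 − 0.05^(1/15) = 18.1%
- 99%: 1 − 0.01^(1/15) = 26.4%

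All three match. The two-sided version would give 18.1%, 21.8% and 29.8%, so the figures are one-sided, as section 3.1 says.

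**Step 2: fewer patients observed to 12 months.** Zero events, same formula, no credit for partial follow-up. The last column is the confidence that 18.1% really carries, 1 − (1 − 0.181)^n.

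| n observed | 90% limit | 95% limit | 99% limit | Confidence carried by 18.1% |
|---|---|---|---|---|
| 15 | 14.2% | 18.1% | 26.4% | 95% |
| 14 | 15.2% | 19.3% | 28.0% | 93.9% |
| 13 | 16.2% | 20.6% | 29.8% | 92.5% |
| 12 | 17.5% | 22.1% | 31.9% | 90.9% |

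**Step 3: credit for time observed.** Assume a constant hazard and k patients lost at 6 months, so that each counts as half a patient: n = 15 − k/2. The 95% limit is 18.7% for k = 1 (n = 14.5), 19.3% for k = 2 (n = 14) and 19.9% for k = 3 (n = 13.5). The increase is about half that in Step 2, in the same direction.

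**Step 4: one toxicity patient replaced.** Suppose one patient has a grade 3 event, does not finish the course and is replaced, and the 15 completers have no event. Among the 15 the result is 0 of 15, with a 95% limit of 18.1%. Among all irradiated patients it is 1 of 16. The exact limit then solves (1 − p)^16 + 16p(1 − p)^15 = 0.05. At p = 0.264 the two terms are 0.0074 and 0.0425, which sum to 0.050, so the limit is 26.4%. This is an illustration of what the replacement rule permits, not a forecast.

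**The case against.** The strongest reply is that the printed limits are correct, openly conditional on 15 patients, and used to justify the cohort size. Section 3.1 also makes the analysis descriptive and insists that the uncertainty be conveyed. Twelve-month observation is plainly intended, since the second group waits for it and entry requires expected survival beyond 12 months. One or two losses move the 95% limit by only 1.2 or 2.5 points. All of this stands, and it limits the size of the point.

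Several stronger readings are tempting but not supported:

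- *A reader might infer that lost patients are scored as event-free.* No text says so; the plan is silent.
- *A reader might infer that 18.1% becomes false after any loss.* The statement is conditional. With fewer observed patients it no longer applies, and it misleads only if quoted unchanged. No window is attached to the rate either; 12 months is inferred from the neighbouring text. For acute events fully observed before a loss, n remains 15.
- *A reader might take these limits as the only numerical statement on toxicity.* Section 3.12 also sets numerical rules: any Grade IV event, and more than 3 of 15 patients with Grade 3.
- *A reader might take the loss rate from the appended ADAS paper.* Its Table 1 has 12-month word-list totals for 40 of 47 and 29 of 45 patients in the trial's MMSE range, or 69 of 92 (75%). The paper does say that "The overall rate of missing data was low but increased with severity of dementia and duration of follow-up", but it includes untestability and recording errors among the causes. An untestable patient can still be examined for toxicity, so 75% does not measure safety attendance.

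On the exclusions, section 3.9 does require all adverse events to be recorded, and a Grade IV event in any patient meets a stopping rule. Monitoring would therefore see these patients. What is missing is a statement that they count in the final safety analysis. For long interruptions the text says they do not. For patients who do not finish, it says only that they are replaced.

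**Conclusion.** The point holds as a gap between two sections, not as an arithmetic error. Section 3.1 needs 15 patients observed for safety over 12 months; section 3.9 secures 15 patients who received radiotherapy as planned.

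The more important consequence is that irradiated patients can be excluded or replaced for reasons that may themselves be toxicity, on a primary safety endpoint. That follows from the rules as written; how often it would happen cannot be judged from the documents.

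The second consequence is modest. For a 12-month rate with zero events, the 95% limit moves from 18.1% to 19.3%, 20.6% or 22.1% with one, two or three patients lost and given no credit, and to 18.7%, 19.3% or 19.9% with half credit. These figures rest on the assumed number of losses, on reading the rate as a 12-month rate and, for the second set, on a constant hazard. The plan should be amended, but the trial's design does not depend on it.

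**What to change.** **Section 3.9.** State that every patient who receives any study radiation stays in the safety analysis and in the event count, even if excluded from or replaced for other endpoints.

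**Section 3.1.**

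- Label the rate as Grade 3 or higher within 12 months.
- State that 14.2%, 18.1% and 26.4% apply only if all 15 patients are observed to 12 months.
- If no event is seen among irradiated patients, report 1 − α^(1/n), with n the number observed to 12 months.
- If any event occurs, report the count over all irradiated patients with an exact limit. Add a Kaplan-Meier estimate of the 12-month rate to handle early losses.

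A denominator made up of patients who either had an event or reached the 12-month assessment should be avoided. It keeps early events but drops early event-free losses, so the rate is biased upward once an event occurs.

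The cost is a few sentences and a short table of limits by n. No extra patients or visits are needed. The drawback is a slightly less favourable limit when patients are lost.
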